A Case Record File will document the research team's telephone 'screening' conversation with the patient. This will commence with a check that the patient has received the PIS and is happy to answer some initial screening questions over the telephone.

Patients will be asked to complete two questionnaires over the telephone, appendix 1 (Rome IV) to assess current symptoms of IBS (Both abdominal pain and altered bowel habit), and Questionnaire (Appendix 2) to confirm malfermentation. If the responses deem them suitable for inclusion and they have none of the exclusion criteria they will be invited to attend a research appointment at the JCRF. Where there is doubt as to a patient's potential eligibility the CI/PI will be asked for a view before the patient is invited for an appointment.

Patients will be asked to bring a urine and stool sample to the screening visit. The research team will post collection kits to the patient in advance with information on collection of the sample. The stool sample will be processed by Microba Laboratory in Brisbane, Australia and the urine sample will be analysed by [name] at Brunel University, Uxbridge. Chain of custody and storage will be maintained as required for the samples. Stool sample collection is easy, just requires a smear of stool sample from toilet paper onto a swab, and then placed in a pouch sealed and brought into the clinic. The sample does not go in the fridge but stays at room temperature until they attend clinic and it will be frozen at -20 for subsequent batch dispatch to the laboratory.

Research Clinic Visit

On arrival at clinic, the research nurse will confirm that the patient has received the PIS and discuss the study with the patient. The research nurse will answer any initial questions that the patient may have and confirm eligibility criteria.

At this clinical appointment and the eligibility, criteria discussed previously by telephone will be confirmed during this appointment.

We plan to recruit at least 20 subjects who complete the study. In case of dropouts, we would plan to recruit up to 30 subjects to accommodate subjects that withdraw or are lost to follow up.

Inclusion Criteria:

1. Aged 18-65
2. Current symptoms of IBS (abdominal pain and altered bowel habit) ROME IV criteria
3. Prepared to take ERME (JUVIA) for duration (taste test available for patient)
4. Normal full blood count within last 12 months (from medical notes if available)

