3. A urine sample will be collected at baseline and frozen to be sent to [name], Brunel University Uxbridge for determination of bacterial metabolites by SIFT/MS (specific ion flow tube mass spectrometry). A faecal sample will also be collected and stored prior to sending to Microba in Brisbane, Australia and again at week 4 for microbial analysis.
4. ERME (labelled as JUVIA) a total of 40mls daily (to be taken with meals) Subjects will be supplied with 3 x 450ml containers of JUVIA. Muntons Maltsters of Stowmarket Suffolk will supply the product to our current packers Chyialis Creation house [name]. On receipt of the product from the supplier details will be entered onto an accountability log at JCRF, and stored appropriately. The product will be stored by the research team in a cool (<25 degrees C), dry and secure environment.
5. The participants will be given enough product (JUVIA) to last for 4 weeks and instructed how to take the product with food daily (20mls at breakfast and 20mls with last meal of the day).
6. Patients will be provided with information as to how to store the product at home and asked to contact the team if they have any concerns.
7. Participants will be asked to complete the IBS severity score questionnaire and IBS Quality of Life Questionnaire at 2 weeks and 4 weeks post their first research hospital appointment. A member of the research team will telephone the patient to remind them to do this and, if preferred, can complete the 2-week questionnaires with the patient over the telephone. Week 4 will be undertaken when they attend the final clinic visit.
8. Patients will be made aware that due to the effects of JUVIA, they may

experience bacterial 'die-offs' when essential nutrients for these bacteria are no longer available in the gut, where symptoms are exacerbated during the first few days and encouraged to continue as symptoms will settle.

9. At 4 weeks post Visit 1, a final hospital (Visit 2) will take place and the same procedures undertaken at Visit 1 will be repeated. A further faecal and urine sample will be collected and urine again frozen prior to transporting to the laboratory for analysis.
10. IBS severity score, IBS QoL questionnaires, Nijmegen and will again be completed at week 4 and the patient will be weighed.

4 Adverse Events and Patient withdrawal

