1. It is unlikely that malt extract, which is already widely used in the food industry, will cause any major difficulties or unwanted effects. In the unlikely event that the patient becomes ill while participating in the study they must report this to the Research team at JCRF, Swansea Bay University Health Board who will discuss with the Chief Investigator/Principal investigator whether or not the participant should be withdrawn from the study.

Adverse events will be collected by asking patients about their symptoms during enrolment in the study. The adverse event will be recorded and reported following the Sponsor's normal procedures.

In the event of a Serious Adverse Event in a patient taking part in the study, the Sponsor's normal reporting procedures apply.

Should the participant find the product unpalatable or unacceptable, they will be asked to remain in study follow-up if they are prepared to do so. If a patient stops taking the product then this must be recorded, along with the reason why. Where patients are agreeable the research team will follow up with them 2 weeks after stopping the product and patients will be asked for permission to use the data and samples already collected to that point, together with any subsequent follow-up data.

If the participants wish to withdraw at any point during the study for whatever reason, they will be asked to remain in follow-up and to allow any data and/or samples collected to that point to be included in the analysis. Participants are free to withdraw without prejudicing their future care and details of withdrawal will document in the Case Record Form.

5 Treatment preparations

ERME (Enzyme rich malt extract) – JUVIA – marketed food supplement. 450mls per bottle

40 mls daily JUVIA provided by Muntons, maltsters of Stowmarket and repacked by Chrysalis. Each subject will be given 2 bottles of JUVIA.

6 Samples

Stool Analysis plan

Faecal samples will be stored before being sent as a batch to Microba Brisbane,

Australia for genomic assay using the Shotgun technique for analysis of the microbiome and comparison with their extensive data collection. Microba have developed and validated a method of faecal sampling which involves taking a smear from lavatory paper and storing it in a specially developed container. Full chain of custody will be maintained.

Urine sample

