8.4 Record Retention

The investigator will maintain confidential all study documentation, and take measures to prevent accidental or premature destruction of these documents.

The documents will be retained in accordance with regulatory guidelines and those of its institution. Records will be stored in the JCRF, prior to off-site storage at a long-term storage facility.

The Investigator will notify the Sponsor prior to destroying any study essential documents following the Clinical Trial completion or discontinuation.

9 General statistical considerations

All baseline, disposition, protocol compliance, exposure and outcome variables (efficacy, safety and exploratory) will be listed and summarized.

The standard summary statistics for continuous baseline and outcome variable are N.mean, standard deviation, median, quartiles, minimum and maximum. The standard summary statistics for categorical baseline and outcome variable are: count and proportion (expressed as percentage).

Sample size calculation

No formal sample size has been calculated for this pilot study.

Endpoints

Primary Efficacy Endpoints

The primary endpoint is the change in IBS severity score from baseline (visit 1) to four weeks (visit 2).

Secondary Efficacy Endpoints

The secondary efficacy endpoints comprise the change in IBS severity score from baseline at two and four weeks will include:

- 1 Severity of abdominal pain
- 2 Frequency of abdominal pain
- 3 Change in abdominal bloating
- 4 Change in bowel habit "satisfaction"
- 5 Change in impact of IBS upon lifestyle
- 6 Change in bowel frequency
- 7 Change in stool consistency
- 8 Change in absence from work days related to IBS (as defined by IBS severity score scales)
- 9 Change in IBS QoL Questionnaire Scores.

Safety Endpoints

The safety endpoints are the incidence, nature, severity, relatedness, duration,

outcome, seriousness and expectedness of treatment emergent adverse events.

Missing Data

Subjects with missing efficacy data will be analysed on a last-observation-carried-forward basis.

8 Study conduct

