Any protocol deviations will be categorized as ‘major’ or ‘minor’, listed, and summarized. All subjects will be given a unique patient identifier number at time on consent which will be used to record all data on the CRF and study database. This ensures patient confidentiality and only staff involved in the study will have access to this database. The database will be shared with the study statistician, who will not have any linked patient identifiers.

The sponsor company representative will be given access to relevant patient information for the purpose of study monitoring to ensure the study and subjects have been recruited and managed in accordance with the protocol and REC approval.

9 Efficacy analysis

Summary statistics will be presented for each efficacy endpoint at baseline, two and four and for the change from baseline at two and four weeks.

10 Safety analysis

The incidence, nature, severity, relatedness, duration, outcome, seriousness and expectedness of treatment emergent adverse events will be listed and tabulated. Reporting of events will be as outlined in Appendix 6.

11 Exploratory analysis

This may include but not limited to:

- Analyzing completing subjects only, repeating parametric analyses using non-parametric analyses, analyzing using a longitudinal model, and investigating different methodologies for adjusting for missing values.

12 Funding

The study will be funded by Ateria Health Ltd. As the sponsor, they have confirmed patient indemnity with CAN Insurance Co. Ltd. For £5,000,000.

13 Reporting and Publication

A final report will be completed and either a full report or summary will be submitted to the REC and R&D after perusal and consent from the Sponsor.

It is intended to publish the results whether positive or negative, in both abstracts and major gastroenterological journals.

14 References

1. Forbes AL Hunter J O Irritable Bowel Syndrome *Medicine* 35 267-271 2007
3. Editorial: balancing fibre and FODMAPs in IBS - a 'rye' look at an old problem. Quigley EM. *Aliment Pharmacol Ther.* 2016 Nov;44(10):1134-1135. doi: 10.1111/apt.13805.

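### Carrying the last observation forward is the only stated rule for missing efficacy data and can bias the mean 4-week change in either direction

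*Protocol*

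**What the plan says.** Protocol section 9 (General statistical considerations, Missing Data) states: "Subjects with missing efficacy data will be analysed on a last-observation-carried-forward basis". The rule covers every efficacy endpoint, including the primary one, which is the change in IBS severity score from visit 1 to week 4. It does not distinguish reasons for missingness, and it does not say whether a baseline score may be carried.

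On timing, section 3 (Study Procedures, item 7) says: "Participants will be asked to complete the IBS severity score questionnaire and IBS Quality of Life Questionnaire at 2 weeks and 4 weeks". There is no other scheduled post-baseline score.

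On numbers, section 2 (Research Clinic Visit) says "We plan to recruit at least 20 subjects who complete the study" and, for dropouts, "we would plan to recruit up to 30 subjects to accommodate subjects that withdraw or are lost to follow up".

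On stopping, section 4 asks subjects who find the product unacceptable, and those who withdraw, to remain in follow-up. It adds: "Where patients are agreeable the research team will follow up with them 2 weeks after stopping the product". It does not say which questionnaires are completed at that contact.

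The alternatives appear only in section 11 (Exploratory analysis), as work that may be done: a completers-only analysis, and "analyzing using a longitudinal model, and investigating different methodologies for adjusting for missing values".

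**The concern.** Last-observation-carried-forward (LOCF) is right for the mean only if, on average, the missing subjects' week-4 scores equal their last recorded scores. Nothing in the protocol supports that. With one carried value per missing subject, the reported 4-week change becomes a mixture of true week-4 changes, week-2 changes and, on the literal reading, zeros for subjects with no post-baseline score. The filled-in values are also counted as observed data when the SD is calculated.

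The study has a single arm and its efficacy result is descriptive, so the mean change and its SD are the result. No comparison group exists in which the error might partly cancel. A later trial sized from this SD would inherit any shrinkage.

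**Working it through.** The protocol states no effect size, SD or sample size calculation, so there is no figure of its own to reproduce. The check is the bias of the mean under LOCF.

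**Inputs from the protocol.** Scores at baseline, week 2 and week 4 (section 3); at least 20 completers and up to 30 recruited (section 2). If exactly 20 of 30 complete, 10 of 30 (33%) lack week 4. That is a ceiling, so 3 and 6 missing are shown as well.

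**Assumed inputs.** All score changes, and an SD of change of 80. A negative change is improvement.

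**Formula.** Bias (LOCF minus true) = (m/30) × (carried change − true week-4 change in those missing).

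| Missing subjects (assumed) | Carried | True week 4 | m = 3 | m = 6 | m = 10 |
|---|---|---|---|---|---|
| Lost after week 2, still improving | −40 | −80 | +4.0 | +8.0 | +13.3 |
| Lost after week 2, worse and then better | +20 | −50 | +7.0 | +14.0 | +23.3 |
| Lost after week 2, benefit wanes | −80 | 0 | −8.0 | −16.0 | −26.7 |
| Baseline only, truly improved | 0 | −50 | +5.0 | +10.0 | +16.7 |
| Baseline only, truly worse | 0 | +50 | −5.0 | −10.0 | −16.7 |

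Positive entries understate the benefit and negative entries overstate it. The first row is the 40-point gap: 3/30 × 40 = 4.0 and 10/30 × 40 = 13.3.

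**Which method does better depends on who is missing.** Take 20 completers with mean −80 and 10 baseline-only subjects whose true mean change is +50:

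- True mean: (20 × −80 + 10 × 50)/30 = −36.7.
- LOCF, baseline carried: (20 × −80 + 10 × 0)/30 = −53.3.
- Completers only: −80.
- A longitudinal model without further scores from the 10: also about −80, if their baselines resemble the completers'.

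If instead the 10 truly changed by −80, the true mean is −80. LOCF still gives −53.3, and the other two are right.

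**SD in the +50 example.** Using expected within-group sums of squares and group means:

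- All true values: (19 × 80² + 9 × 80² + (20 × 10/30) × 130²)/29 = (179,200 + 112,667)/29 = 10,064, so SD ≈ 100.
- LOCF with ten zeros: (19 × 80² + (20 × 10/30) × 80²)/29 = (121,600 + 42,667)/29 = 5,664, so SD ≈ 75.

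A simulation of 20,000 runs gave 100.6 and 75.0, a ratio of 0.75. The SD is thus about 25% too small in this example. If all 30 had true mean −80 and SD 80, the same ten zeros would give about 75 against 80.

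**The case against.** **The stopper recorded as unchanged.** A reader might infer that early stoppers who worsen are bound to be entered as change 0. The protocol does not establish that. Carrying the baseline is the literal reading but is not stated, and it matters only for subjects with no post-baseline score. Stopping the product is also not the same as being missing, since section 4 asks stoppers to stay in follow-up. The point stands only in conditional form.

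**The early flare.** Section 3, item 8 warns of a phase "where symptoms are exacerbated during the first few days and encouraged to continue as symptoms will settle". This might be taken as proof that scores are not flat. It is weak support: the severity form (Appendix 3) asks about roughly the last 10 days, so a week-2 score looks back to about day 4 (14 − 10). A flare in the first days falls largely outside that window and says little about weeks 2 to 4, the interval over which week-2 scores are carried.

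**The contact after stopping.** A reader might also infer that LOCF would carry a score from this contact. Section 4 does not say that a score is taken there.

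**Scale and setting.** Ten of 30 is a contingent ceiling, not an expected loss. The protocol specifies summary statistics and no test or confidence interval, so claims about interval coverage or error rates do not apply. Exploratory alternatives are listed. All this is fair and limits the size of the concern, but the optional analyses do not displace the rule that produces the main result.

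**The remedy.** The strongest objection is that a model restricted to subjects with a post-baseline score drops exactly those lost before week 2, and in the +50 example does worse than LOCF (−80 against −53.3, truth −36.7). This stands, and it shapes the fix.

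**Conclusion.** The concern holds in limited form. The protocol fixes LOCF as the sole main rule for missing efficacy data without a basis for its assumption, and this can move the mean 4-week change either way and make the SD too small. If the baseline is carried, a subject with no later score counts as zero change whatever happened.

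The size cannot be determined from the protocol. A 40-point gap between carried and true change gives a bias of 4 points at 3 of 30 missing and 13 at 10 of 30. Both the gap and the number missing are assumptions, and the bias is nil if the two changes agree on average. The protocol does not support a conclusion that LOCF will specifically flatter the product.

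**What to change.** 1. **Collect the data.** Ask subjects who stop the product but remain in follow-up for the severity score at the scheduled week-2 and week-4 dates, by telephone or post, and use those scores in the analysis. Keep any score from the contact two weeks after stopping separate, and do not carry it to week 4.
2. **Change the main estimate.** Estimate the week-4 change from a longitudinal model of all observed scores. Enter baseline as one of the repeated measures, so that subjects with only a baseline score are not dropped.
3. **Reorder the sensitivity analyses.** Keep LOCF and completers-only as sensitivity analyses. Add one in which subjects with a missing week-4 score are assigned no change or an assumed worsening. Report the number of missing week-4 scores and the reasons.

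The cost is a short amendment and some posted or telephoned questionnaires. Telephone completion is already allowed at week 2, and a longitudinal model is already listed as exploratory. The downside is that the model relies on data being missing at random. Keeping baseline-only subjects in it does not correct for early stoppers who got worse, so item 1 and the worsening analysis in item 3 are essential parts of the change.

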Appendix 1 (completed at Telephone Screening)
Rome IV

Rome IV Criteria for Diagnosing IBS:

Recurrent abdominal pain, on average, at least 1 day/week in the last 3 months, associated with two or more of the following criteria:

- Related to defecation
- Associated with a change in frequency of stool
- Associated with a change in form (appearance) of stool.

Criteria fulfilled for the last 3 months with symptom onset at least 6 months before diagnosis.

Source: Lacy BE, et al. Bowel Disorders. Gastroenterology. 2016;150:1393-1407; Rome III Diagnostic Criteria for Functional Gastrointestinal Disorders. Accessed 8/10/16 at: http://www.romecriteria.org/assets/pdf/19_RomeIII_apA_885-898.pdf

Questionnaire 2 (completed at Telephone Screening and 4 weeks)
IBS subtype “malfermentation” symptom Questionnaire

IBS SUBTYPE ‘MALFERMENTATION’ SYMPTOM QUESTIONNAIRE

1. Are your stools loose and runny?

Never Score 0	Rarely Score 0	Sometimes Score 1	Often Score 1	Very often Score 2
--------------------------------	---------------------------------	------------------------------------	--------------------------------	-------------------------------------

2. Are your stools hard and pellet like?

Never Score 4	Rarely Score 3	Sometimes Score 2	Often Score 1	Very often Score 0
--------------------------------	---------------------------------	------------------------------------	--------------------------------	-------------------------------------

3. Do you have to rush to the lavatory to open your bowels with great urgency?

Never Score 0	Rarely Score 1	Sometimes Score 2	Often Score 3	Very often Score 4
--------------------------------	---------------------------------	------------------------------------	--------------------------------	-------------------------------------

4. Do you ever have to strain or push to pass a motion?

Never Score 4	Rarely Score 3	Sometimes Score 2	Often Score 1	Very often Score 0
--------------------------------	---------------------------------	------------------------------------	--------------------------------	-------------------------------------

5. Do you ever feel that you have not emptied your bowels completely?

Never Score 4	Rarely Score 3	Sometimes Score 2	Often Score 1	Very often Score 0
--------------------------------	---------------------------------	------------------------------------	--------------------------------	-------------------------------------

A score of 11 or more confirms malfermentation

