In a preliminary study of patients with IBS, symptoms were reduced by ERME in 4 out of 5 patients with partial benefit in the fifth. This was associated with a dramatic reduction in hydrogen excretion on the breath, strong evidence of modified colonic fermentation.

IBS, however, is not a single condition¹. Several mechanisms produce the symptom complex apart from malfermentation. These include anxiety, constipation, (sometimes complicated by overflow diarrhoea) menstrual disturbances and musculo-skeletal problems. These can be separated by validated symptom analyses. We wish to know whether ERME is of any benefit in other IBS sub-groups⁸ and to seek biomarkers in urine and stool samples, which may allow objective identification of these groups, currently separable only by symptoms⁹. This study is designed to concentrate on the malfermentation form of IBS.

2 Patient Identification and Recruitment

This will be a single site study, conducted at the Joint Clinical Research Unit (JCRF),

Institute of Life Science 2, Swansea University, Swansea.

The research team will work with local Gastroenterologists and General Practitioners to identify potential subjects: Patients with a confirmed diagnosis of IBS made by a clinician and be aged between 18 – 65 years. They will also discuss with the IBS dietician group in respect of patients who may be considered for this study.

These potential subjects will be sent a Patient Information Sheet (PIS) and consent form in the post, together with a covering letter from either their local GP or the Consultant Gastroenterologist (whoever is the most appropriate i.e. who has provisionally identified them as suitable for the study). The Information Sheet will contain the contact details of the research team at JCRF and ask patients to get in touch if they would like to know more about the study.

With permission from the Research Ethics Committee to do so, the research team may telephone recipients of the patient information sheet to see whether they have any questions about the study and whether they might be interested in taking part.

Initial Screening by telephone

For any patient who may be interested in taking part, the research team will undertake initial 'screening' over the telephone if this is acceptable to the patient. The purpose of this would be to avoid patients traveling to the hospital unnecessarily (if they do not meet the inclusion criteria).

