5. Previous Calprotectin (from medical notes if available) <80.ug/g
6. Previous tTG (Tissue Transglutaminase) (from medical notes if available)
7. Positive for malfermentation as decided by IBS Questionnaire Score
8. Registered with a GP and consent to GP being informed

Exclusion Criteria:

1. Pregnant, planning to become pregnant or lactating
2. Diabetic (or other co-morbidity which the CI considers inappropriate)
3. On a restrictive diet or unwilling or unable to change diet
4. Current medication (e.g. opiates) that may influence bowel symptoms (at discretion of the CI)
5. Antibiotics in the previous 6 weeks
6. Other gastrointestinal disease (e.g. coeliac, Crohn's disease or Ulcerative colitis)

-
7. Significant gastrointestinal surgery (this will be a clinical decision and any patient who has had a surgical procedure that would change the mechanics of gut function would be excluded)
-
8. Involved in other gastroenterology research project or other interventional study that would affect results
-

Patients who do not meet the entry criteria will not be enrolled into the study, but will attend their routine clinic appointments and or general practitioner care. Patients who meet the inclusion criteria and would like to take part will have eligibility confirmed by the local investigator who will also take informed consent or delegate to the research nurse **Note:** The research team will offer the patient an opportunity to taste the product before enrolling so that they can assess whether they will be able to take the product daily for the 4-week period required.

3 Study Procedures

1. Following telephone screening, informed consent and enrolment, patients will be asked to complete the IBS Severity Score (appendix 3) and IBS Quality of Life Questionnaire (appendix 4). Additionally they will be asked to complete the Nijmegen anxiety questionnaire (appendix 5) & the Cambridge IBS type questionnaire. Demographic data will be collected as per the clinical record form as described in the patient information sheet.
2. Where a patient does not have a faecal calprotectin (FC) result, a test may be requested if the investigator feels it is necessary.

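### The malfermentation cut-off in inclusion criterion 7 is met by a Rome IV patient who answers Never to all five items, so the total alone does not secure the intended population

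*Protocol*

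**What the plan says.** The Introduction states the target population: "This study is designed to concentrate on the malfermentation form of IBS". Inclusion criterion 7 (section 2) puts this into practice as "Positive for malfermentation as decided by IBS Questionnaire Score". It is the only entry criterion that mentions malfermentation.

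The form is the subtype questionnaire printed after the Rome IV criteria in Appendix 1, labelled Questionnaire 2. It has five items, each answered from Never to Very often, and a single decision rule: "A score of 11 or more confirms malfermentation". No minimum is set on any item. Its heading places it at telephone screening and again at 4 weeks.

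Inclusion criterion 2 separately requires current IBS symptoms by Rome IV. Section 9 takes the primary endpoint from the IBS severity score and the secondary endpoints from that score and the IBS-QOL. This questionnaire is not a named endpoint.

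**The concern.** A rule said to confirm a subtype would be expected to need at least one positive sign of it. Here most of the available points come from not having constipation-type symptoms, and those points alone exceed the cut-off. The criterion can therefore admit patients who report neither loose stools nor urgency, the only two items that score upward with symptoms.

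What is at stake is the label on the study population. The protocol plans at least 20 completers and up to 30 recruits, and describes no control arm. One patient admitted on this route would be 1/20 = 5% of a 20-patient analysis. The Introduction also hopes to find urine and stool biomarkers for subgroups that can at present be told apart only by symptoms, so a weakness in the symptom classifier carries into that aim.

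**Working it through.** **Inputs**, all from the printed form:

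| Item | Never | Rarely | Sometimes | Often | Very often |
|---|---|---|---|---|---|
| 1. "Are your stools loose and runny" | 0 | 0 | 1 | 1 | 2 |
| 2. "Are your stools hard and pellet like" | 4 | 3 | 2 | 1 | 0 |
| 3. "Do you have to rush to the lavatory to open your bowels with great urgency" | 0 | 1 | 2 | 3 | 4 |
| 4. "Do you ever have to strain or push to pass a motion" | 4 | 3 | 2 | 1 | 0 |
| 5. Incomplete emptying | 4 | 3 | 2 | 1 | 0 |

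Total = item 1 + item 2 + item 3 + item 4 + item 5; positive if the total is 11 or more. The protocol gives no derivation of the 11, so there is no calculation of its own to reproduce.

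**Where the points come from.** The maximum is 2 + 4 + 4 + 4 + 4 = 18. Items 2, 4 and 5 supply 3 × 4 = 12 of these for the absence of a symptom. Items 1 and 3 supply 2 + 4 = 6 for its presence.

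**Example profiles**

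| Profile (items 1, 2, 3, 4, 5) | Sum | Result |
|---|---|---|
| Never on all five | 0+4+0+4+4 = 12 | positive |
| Items 1 and 3 Often; 2, 4, 5 Sometimes | 1+2+3+2+2 = 10 | negative |
| Items 1 and 3 Very often; 2, 4, 5 Sometimes | 2+2+4+2+2 = 12 | positive |
| Items 1 and 3 Very often; 2, 4, 5 Never | 2+4+4+4+4 = 18 | positive |

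**How many patterns are affected.** Full enumeration of the 5^5 = 3125 answer patterns gives 894 with a total of 11 or more. The affected subset can be counted by hand. Let C be the sum of items 2, 4 and 5.

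- C = 12 arises in 1 way (all Never), C = 11 in 3 ways (one Rarely), and C = 10 in 6 ways (two Rarely, 3 ways; one Sometimes, 3 ways).
- Item 1 Never or Rarely scores 0 either way (2 choices).
- With item 3 Never (0 points), C must be at least 11: 1 + 3 = 4 ways.
- With item 3 Rarely (1 point), C must be at least 10: 1 + 3 + 6 = 10 ways.
- Never or Rarely on both items 1 and 3: 2 × (4 + 10) = 28 patterns, and 28/894 = 3.1%.
- Never on both: 1 × 4 = 4 patterns, and 4/894 = 0.4%.

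**Does Rome IV block the route?** The criteria in Appendix 1 need recurrent abdominal pain plus two of three features: relation to defecation, change in stool frequency, change in stool form. Pain related to defecation together with a change in frequency is enough. Neither feature contradicts Never on any of the five items, so the all-Never patient can pass both gates.

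**Week 4.** Whenever items 2, 4 and 5 are all Never, the total is at least 12. A patient free of all five symptoms is therefore always still positive. The same total of 12 is reached by the third profile above, which has very frequent loose stools and urgency.

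**The case against.** The best defence is that the form is meant to separate subtypes among people who already have IBS. The Introduction ties abnormal fermentation to wind and discomfort, does not define it by loose stools, and lists constipation among the other mechanisms. A score weighted towards the absence of constipation fits that purpose. On this reading, turning away the patient who scores 10 may be intended, because that patient sometimes has hard stools, straining and incomplete emptying. This stands as far as it goes: the rejected profile shows how the score ranks patients and is not a separate error. It does not explain why the form should treat malfermentation as confirmed in someone who reports none of the five symptoms.

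The route is also narrow. Rome IV applies, doubtful cases go to the chief or principal investigator, and the local investigator confirms eligibility. These safeguards reduce the risk, but none sets a minimum on items 1 or 3.

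A reader might infer three stronger points that the protocol does not support.

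- *Item 1 is misprinted*, because it runs 0, 0, 1, 1, 2 while the others span 0 to 4. Unequal weights are not an error in themselves, and nothing in the text shows a slip. Only the source instrument could settle this.
- *The questionnaire cannot register recovery.* This is true only of positive or negative status after complete resolution. The raw total can fall, at most from 18 to 12.
- *The week-4 result is compromised.* No analysis of the week-4 questionnaire is stated, and the week-4 list in section 3, item 10 does not name it.

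**Conclusion.** The eligibility point holds and should be fixed. As printed, criterion 7 can be met with no loose stools and no urgency, in a study that says it concentrates on malfermentation. The arithmetic is exact and rests only on the printed item scores and cut-off.

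Its reach is small in terms of patterns: 28 of 894 qualifying patterns, or 4 of 894 on the strictest count. How many patients this means is unknown, because real answers are not spread evenly over patterns. Nor are those admitted free of symptoms, since Rome IV still requires pain. The primary endpoint uses another instrument and remains computable; what is weakened is the claim about whom it describes. For a descriptive pilot, that makes this a correction worth making rather than a defect that invalidates the plan.

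The week-4 point is secondary and conditional: the 11-point cut-off would mislead only if someone used it to judge response.

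**What to change.** 1. Before recruitment, check the five sets of item scores and the cut-off of 11 against the source instrument, and correct any discrepancy. This comes first, because the remedy should not rest on a reviewer's own definition of the subtype.
2. If the scores and cut-off stand as printed, amend inclusion criterion 7 so that the total alone does not suffice and some positive response on item 1 (loose stools) or item 3 (urgency) is also needed. The sponsor should set the level and give the reason. This closes the all-Never route. It does not change the result for the patient scoring 10, which the sponsor should confirm is intended.
3. If the week-4 questionnaire is reported, do not treat crossing the cut-off as response. Show items 1 and 3 separately.

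The cost is one check, one eligibility sentence and, if used, one reporting line. The downside is that a few telephone-screened patients would become ineligible. The change belongs before enrolment: patients wrongly admitted could be set aside later, but those wrongly turned away leave no outcome data.
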